 - O Increased B-type natriuretic peptide (BNP)/ N-terminal pro-BNP (NT-proBNP) concentrations consistent with decompensation of heart failure (such as BNP > 500 pg/mL or NT-proBNP > 2,000 pg/mL). In patients with chronically elevated natriuretic peptides, a significant increase should be noted above baseline.
 - o Radiological evidence of pulmonary congestion.
 - Non-invasive diagnostic evidence of clinically significant elevated left- or rightsided ventricular filling pressure or low cardiac output. For example echocardiographic criteria could include: E/e' > 15 or D-dominant pulmonary venous inflow pattern, plethoric inferior vena cava with minimal collapse on inspiration, or decreased left ventricular outflow tract minute stroke distance (time velocity integral).
 - o Invasive diagnostic evidence with right heart catheterization showing a pulmonary capillary wedge pressure (pulmonary artery occlusion pressure) ≥ 18 mmHg, central venous pressure ≥ 12 mmHg, or a cardiac index < 2.2 L/min/m2

- 5) The patient receives initiation or intensification of treatment specifically for HF, including at least ONE of the following:
 - a. Augmentation in oral diuretic therapy.
 - b. Intravenous diuretic or vasoactive agent (e.g., inotrope, vasopressor, or vasodilator).
 - c. Mechanical or surgical intervention, including:
 - Mechanical circulatory support (e.g. intra-aortic balloon pump, ventricular assist device, extracorporeal membrane oxygenation, total artificial heart).
 - Mechanical fluid removal (e.g., ultrafiltration, hemofiltration, dialysis).
- **Urgent visit for HF:** any unplanned visits for HF decompensation resulting in intravenous therapy for HF, including diuretic or inotropic drugs.
- **Death:** All deaths reported post-randomization, except for patients who have withdrawn their consent, should be adjudicated. Deaths will be sub-classified by CV, non-CV primary cause or undetermined cause of death. Classification of deaths as CV or non-CV is aimed at capturing the primary cause of death. The primary cause as defined here is the underlying disease or injury that initiated the train of events resulting in death.
- Cardiovascular (CV) death: CV deaths include deaths that result from an
 myocardial infarction, sudden cardiac death, death due to HF, death due to
 stroke, death due to CV procedures, death due to CV hemorrhage, and death due
 to other CV causes (31).

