- 9. Does the patient meet all the inclusion criteria and none of the exclusion criteria? (Yes / No, they can only be randomized if yes is selected).
- 10. Has the patient signed informed consent? (Yes / No, they can only be randomized if yes is selected)

Data will be stored in a secure server located at the Coordinator Center (Hospital Álvaro Cunqueiro, Vigo) and will be kept confidential according to legal regulations for data protection.

FOLLOW-UP STRATEGIES

Follow-up will consist on telephone calls and review of patients' medical records.

Once a local investigator identifies that a patient has been admitted for something potentially relevant to the study, he/she will be responsible for collecting the information (admission report, tests, etc..) and send it blinded to the central site for blinded event adjudication.

Follow ups will be done at 2 timepoints: 3 ± 1 , 12 months.

PATIENT ENGAGEMENT / RETENTION STRATEGIES

After randomization, each patient will receive a card identifying the clinical trial that will contain a brief explanation of the aims of it. In the trial card, the arm in which the patient was included (dapagliflozin yes or no) will be stated, together with a central telephone number and email. The patient will be encouraged to contact (phone call/email) for any question related to the trial (either from the patients or from any physician seeing the patient). Any change related to dapagliflozin therapy (stop or initiate dapagliflozin) will be ideally communicated before implementation so the research team can annotate the reasons for the change. Moreover, any change in clinical status (admissions, symptoms, etc..) related to the study may be reported using this telephone number or email. Patients will be asked to carry the study card always with them to facilitate interaction.

No incentives will be established for participating in the study.

PARTICIPANT WITHDRAWAL

Given that this is an open label study with an approved medication and crossovers are not a criterium for withdrawal from the study (see below), the only reason for patient withdrawal from the study is the willingness of the patient to be excluded from the trial.

CROSSOVERS

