- General monitoring. All patients will receive the usual follow-up performed at their center for patients after TAVI. Once a potential event is detected either by a

local investigator, a report from the local investigator should be sent to the coordinating center for the evaluation by the adjucation committee.

Specific data: Al investigators will be encouraged to report information about ECG, analytical, and echocardiographic data throughout the first year.

DATA SAFETY MONITORING BOARD (DSMB)

A Data Safety Monitoring Board (DSMB) will be established to formally review the accumulating data from this trial to ensure there is no avoidable increased risk for harm to subjects. Two interim analyses will be performed on primary endpoint and secondary safety endpoints when 33% (81) and 66% (172) of events have been adjudicated (see interim analysis section below). The DSMB will be chaired by an academic cardiologist who is an expert in TAVI care and statistical analyses in clinical trials.

STUDY SCHEDULE

- **SCREENING:** During hospitalization for TAVI.
- ENROLLMENT/BASELINE. At discharge, randomization will take place and baseline patient data will be recorded. The investigator must ensure that the patient signs the informed consent, meets the inclusion criteria and has no exclusion criteria.
- **OPEN-LABEL TREATMENT PHASE:** 2 years.
 - FOLLOW-UP. At 3±1 and 12 months. Clinical follow-up (telephone and medical history revision) will be performed to detect any potential event (end-points and adverse events). To report data about echocardiography and laboratory tests during the first year will be optional
 - o FINAL FOLLOW-UP. 1 year after last patient enrolment. All patients underwent 12 months follow-up.
 - o EARLY TERMINATION VISIT. In case the patient leaves the study ahead of time (due to personal decision), a clinical follow-up (telephone and medical history) will be performed at the time of leaving the study.

	SCREENING	ENROLLMENT	STRATEGY	
	During admission	At discharge	After d Month 3±1	ischarge Month 12
Administrative data				
Inclusion/exclusion criteria	Х			
Informed consent		X		
Demographic		X		
Clinical data				
Medical history		X		
Data about TAVI		X		
Physical examination		X		
Medication history		X		
ECG		X	X*	
Echocardiography		X	X*	
Laboratory data		X	X*	
Medication at discharge		X		
Drug (dapagliflozin yes/no)				
Randomization		X		
Follow-up				
Vital status			X	X
Events of end-point			X	X
Adverse events			X	X

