> Assumptions:

- Overall alpha value: 0.05
 - o Haybittle-Peto approach for interim monitoring
 - 1st interim analysis: alpha value of 0.001
 - 2nd interim analysis: alpha value of 0.001
 - Final analysis: alpha value of 0.05
- Power: 0.80.
- Test: log-rank (superiority two-sided)
- Minimal treatment effect: HR 0.70.
- 1-year incidence of primary endpoint (controls): 30%
- Accrual period: 2 years
- Follow-up period: 1 year for all patients.
- Percentage of subjects anticipated to withdraw: 5%
- Number of expected primary endpoints: 260.
- > Sample size: 1,020 participants

ADAPTIVE SAMPLE SIZE: The sample size for this study was based on the anticipated incidence of the composite endpoint. It is anticipated that the 1-year incidence of the primary endpoint will be 30% in the control arm and 21% in the dapagliflozin arm (thus, 25.5% in the overall population). To reduce the chances of having an underpowered study secondary to an event rate lower than predicted, a blinded examination of the study overall event rate will be done 3 months before closing the recruitment. At that moment, it is anticipated that >400 patients already underwent 12 months follow-up. In the case that the overall event rate is below 25%, the DSMB will discuss the possibility to doing a re-calculation of sample size according to actual event rate, and the chair will decide if it is needed to increase sample size (thus

extend recruitment period). As this analysis will be performed in a blinded fashion, adjustment for multiplicity is not required and will not be applied.

INTERIM ANALYSIS

Two interim analyses will be performed on primary endpoint and secondary safety endpoints when 33% (86) and 66% (172) of events have been adjudicated. Efficacy and safety interim analyses will be performed following the same methodological guidelines described in this document for the final analysis. Stopping rules for efficacy analysis will be based on the statistical Haybittle-Peto approach, with an overall alpha value 0.05. Safety analyses will be addressed by applying descriptive statistical methods to the data, supplemented by calculation of confidence intervals. No formal statistical stopping rules for safety data will be predefined.

REDUCING BIAS

• Randomization:

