Primary analyses will be performed in the "full data set" in an intention-to-treat fashion. The intervention arm will be compared against the control arm for the composite primary endpoint. Time-to-event will be evaluated using the Kaplan-Meier survival analysis followed by multivariable Cox proportional hazards model. Hazard ratios (HR) with corresponding 95% confidence intervals will be calculated for treatment effect estimation. All patients without an event will be censored at last day of follow-up. Patients that withdraw from follow-up will be considered censored on the day of withdrawal. Due to the randomization process and the large sample size of the trial, it will be not expected the presence of covariate relevant imbalances between treatment groups. However, for exploratory purpose, standardized differences will be calculated. Those known prognostic factor presenting an imbalance higher than 0.1 standardized difference will be included in the multivariable Cox model. For all tests, we will use 2-sided p-values with alpha ≤0.05 level of significance.

SECONDARY ANALYSIS

The secondary endpoints will be the individual components of the primary composite endpoint, besides CV mortality and the development of new atrial fibrillation. Analyses will be performed following the same guidelines described for primary analysis. Multiplicity adjustment will be not implemented because the hierarchical structure between primary and secondary endponits.

To better explore the treatment effect under ideal circumstances (explanatory approach), primary and secondary endpoint analyses will be replicated in the "per protocol data set" using same methods described above.

SUBGROUP ANALYSIS

All subgroup analyses will be performed using interaction models based on the primary analysis model, also including the subgroup in question and the treatment-subgroup interaction as factors, and presented as treatment hazard ratios for each subgroup and the interaction p-value. Subgroups will be specified in the endpoints section below.

PRE-SPECIFIED SUB-GROUP ANALYSES

- > Diabetic vs non-diabetic patients.
- ightharpoonup LVEF < vs > 40%.
- \geq 80 years vs < 80 years of age on recruitment
- ➤ Males vs females
- ➤ Atrial fibrillation versus sinus rhythm
- > Hypertensive vs normotensive patients
- ➤ Moderate-severe vs mild LVH.
- > Treatment with beta-blockers vs. no beta-blockers

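### Patients who leave the study are censored that day even if they would still allow record review; the effect on the primary hazard ratio is small and conditional

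*Combined protocol and SAP*

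**What the plan says.** Four places bear on this, all in the combined protocol and SAP, and they do not use the same term.

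- Primary Analysis: "Patients that withdraw from follow-up will be considered censored on the day of withdrawal". The trigger is leaving follow-up. The Secondary Analysis section applies the same rules to the secondary endpoints.
- Definition for Evaluations of Events During Follow-up, Death: "All deaths reported post-randomization, except for patients who have withdrawn their consent, should be adjudicated". Here the trigger is narrower: withdrawal of consent.
- Participant Withdrawal: "the only reason for patient withdrawal from the study is the willingness of the patient to be excluded from the trial". No partial form of withdrawal is described.
- Study Schedule, early termination visit: for a patient who leaves early by personal decision, "a clinical follow-up (telephone and medical history) will be performed at the time of leaving the study". Nothing is scheduled after that.

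Two other provisions set the limits of the issue. Follow-up Strategies and Follow-up Procedures use both telephone calls and medical records. Crossovers states that patients who stop or start dapagliflozin remain in the trial, are followed as planned and are analysed as randomized.

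**The concern.** The analysis rule censors a wider group than the adjudication rule excepts. A patient can leave the study without refusing the use of records, and the plan never asks. For such a patient a later death or heart-failure admission could be found by the record review that sites already do, yet the censoring rule would leave it out of the primary endpoint.

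The trial is open-label with no placebo, and leaving is entirely the patient's choice. It may therefore depend on arm and on prognosis. Censoring at withdrawal in the Kaplan-Meier and Cox analyses is unbiased only if, within each arm, those who leave have the same later risk as those who stay. The plan has no sensitivity analysis for departures from this; its only alternative analysis, per protocol, censors more patients. At stake are a few primary events and a possible shift in the primary hazard ratio, in either direction.

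**Working it through.** **Inputs from the Sample Size section.** Two-sided log-rank test, alpha 0.05, power 0.80, "Minimal treatment effect: HR 0.70", one-year incidence 30% (control) and 21% (dapagliflozin), 25.5% overall, one year of follow-up for everyone, 5% withdrawal, 1,020 patients, 260 expected events. The 5% is not split by arm.

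**Step 1: reproduce the plan's figure.** Schoenfeld: D = 4(1.960 + 0.842)² / (ln 0.70)² = 246.8, so 247 events. 247 / 0.255 = 968.6, so 969 patients. 969 / 0.95 = 1,020, an exact match. The 260 events are 1,020 × 0.255 = 260.1, the count if withdrawal costs no events.

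**Step 2: precision.** Suppose all 5% (51 patients) left on day 0 at average risk. The loss is 51 × 0.255 = 13.0 events, leaving 247. Power = Φ(|ln 0.70| × √D / 2 − 1.96), which is 80.0% at D = 247 and 82.0% at D = 260. The inflation for 5% withdrawal already covers this.

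**Step 3: events lost.** Assume exponential event times, leaving spread evenly over the year, and 25.5 leavers per arm. The control hazard is −ln 0.70 = 0.357 per year. At a hazard ratio of 0.70 the dapagliflozin hazard is 0.250 and its one-year incidence is 22.1%, so full follow-up gives 510 × (0.300 + 0.221) = 266 events. For a leaver with hazard h, the chance that the first event falls after leaving is (1 − e^(−h))/h − e^(−h).

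- Average risk: control 0.841 − 0.700 = 0.141; dapagliflozin 0.885 − 0.779 = 0.106. Loss = 25.5 × (0.141 + 0.106) = 6.3 events.
- Three times the risk (h = 1.070 and 0.749): 0.271 and 0.231. Loss = 25.5 × 0.502 = 12.8 events.

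**Step 4: hazard ratio.** Randomization balances risk, so place the same high-risk subgroup, 8% of patients with k times the hazard of the rest, in each arm. Draw all leavers from it, keep control incidence at 30%, set the hazard ratio to 0.70 within each risk group, and solve the large-sample Cox score equation with and without censoring at leaving.

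| Leaving, dapagliflozin / control | k | HR, full follow-up | HR, censored at leaving | Events lost |
|---|---|---|---|---|
| 5% / 5% | 2 | 0.702 | 0.701 | 9.9 |
| 5% / 5% | 3 | 0.706 | 0.704 | 12.1 |
| 8% / 2% | 1 | 0.700 | 0.700 | 5.8 |
| 8% / 2% | 2 | 0.702 | 0.686 | 9.2 |
| 8% / 2% | 3 | 0.706 | 0.678 | 11.5 |
| 2% / 8% | 1 | 0.700 | 0.700 | 6.8 |
| 2% / 8% | 2 | 0.702 | 0.717 | 10.6 |
| 2% / 8% | 3 | 0.706 | 0.731 | 12.8 |

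A second construction fixes each arm's one-year incidence (30% and 22.1%) and gives leavers k = 2 or 3 times their arm's average hazard. It yields 0.682 and 0.668 for the 8%/2% split, and 0.716 and 0.724 for 2%/8%. Equal withdrawal moves the ratio by about 0.003 or less in either construction.

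**Step 5: scale.** With 260 events the standard error of the log hazard ratio is about 2/√260 = 0.124. The unequal splits in the table shift it by ln(0.717/0.702) = 0.021 to ln(0.706/0.678) = 0.040, that is 0.2 to 0.3 standard errors. With no true effect, the second construction and an 8%/2% split give an apparent ratio of 0.96 to 0.98 and a one-sided error in the favoured direction of 3.9% to 5.0% instead of 2.5%.

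**The case against.** The strongest reply is that the plan already handles the main reasons for arm-dependent exit. Side effects on dapagliflozin, or a wish for the drug in the control arm, lead to crossover, and crossovers stay in follow-up. The adjudication exception is limited to withdrawn consent, where censoring is appropriate. The 5% inflation covers the lost precision. All of this stands, and it narrows the point to patients who leave the study without refusing record use.

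Several stronger readings are tempting but unsupported:

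- *Withdrawal ends all data collection.* No sentence says so. A check takes place at leaving, and the text is silent on what follows.
- *Deaths after withdrawal are barred from adjudication.* The exception covers only patients who withdrew consent.
- *Arm-dependent censoring will occur.* The documents give 5% overall and say nothing about arm or prognosis.
- *Records could certainly be used afterwards.* That depends on permission. The consent form is not among the pages available here, so its terms cannot be judged.
- *The true hazard ratio could be 0.74 to 0.77, or 0.65 to 0.67, and be misreported.* Such values arise only if unequal numbers of high-risk patients are placed in the two arms, which randomization rules out in expectation.
- *No analysis could address the problem.* Weighting or tipping-point analyses could bound it, although they cannot replace uncollected events.

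**Conclusion.** The concern holds in limited form. The censoring rule reaches further than the consent-based exception in the Death definition, and it discards events that existing record review could supply for leavers who would allow it. The size is about 6 to 13 primary events at 5% withdrawal, taking leavers at one to three times average risk and leaving spread evenly over the year. Bias requires two conditions together: withdrawal that differs by arm, and leavers whose risk differs from that of stayers. The documents establish neither. Under the assumed 8%/2% split with two to three times the risk, a hazard ratio of about 0.70 would be reported as about 0.68 (0.67 to 0.69 across the two constructions) if more leave dapagliflozin, or about 0.72 to 0.73 if more leave control. The figures treat every leaver as someone who would have allowed record review, so they are upper limits for each scenario. The change is worth making because it is cheap and because uncollected outcomes may not be recoverable later.

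**What to change.** 1. In Participant Withdrawal and in the early termination visit of the Study Schedule: ask each withdrawing patient at that contact whether review of records and vital status may continue to month 12, and record the answer and its date in the eCRF.
2. In Primary Analysis: censor at withdrawal only patients who refuse, treating refusal as full withdrawal of consent so that the rule matches the exception in the Death definition. Follow the others through records to month 12 and count their events as randomized.
3. In the Death definition: state that the exception means this full withdrawal.

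The cost is one consent-form and eCRF item plus wording in these sections, using record review that sites already do. The drawback is that some patients will have outcomes from records only, without NYHA class or call data.

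### Chance imbalance above 0.1, among prognostic factors that are never listed, chooses the covariates of the primary Cox model; a fixed list of fields entered at randomisation would be the better and usually more powerful choice

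*Combined protocol and SAP*

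**What the plan says.** The Primary Analysis section describes the method as follows: "Time-to-event will be evaluated using the Kaplan-Meier survival analysis followed by multivariable Cox proportional hazards model". On the role of the hazard ratio it says: "Hazard ratios (HR) with corresponding 95% confidence intervals will be calculated for treatment effect estimation". It expects no relevant imbalance, then adds: "However, for exploratory purpose, standardized differences will be calculated". The next sentence makes those differences select the model: "Those known prognostic factor presenting an imbalance higher than 0.1 standardized difference will be included in the multivariable Cox model".

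No section lists the factors that count as known prognostic. The baseline table under Data Recording has about 30 variables to collect, and the pre-specified subgroups form another list; neither marks candidates for adjustment.

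Other analyses inherit the rule:
- Secondary endpoints: "Analyses will be performed following the same guidelines described for primary analysis". The per-protocol repeat uses the same methods.
- Subgroups: "All subgroup analyses will be performed using interaction models based on the primary analysis model".
- Interim looks: "Efficacy and safety interim analyses will be performed following the same methodological guidelines described in this document for the final analysis".

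The log-rank test appears once, among the Sample Size assumptions: "Test: log-rank (superiority two-sided". The alpha levels stand in the same list. The Primary Analysis section does not mention the log-rank test.

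Diabetes status, age, sex, creatinine and LVEF are all fields that must be completed before an allocation is issued (Randomization and Strategies for Recruitment; Randomization System).

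**The concern.** Under randomisation, an observed imbalance is chance. It is a weak reason to adjust, because what an adjusted analysis gains depends on how strongly a variable predicts the outcome. A rule keyed to imbalance leaves out strong predictors that happen to be balanced and lets in weak ones that happen not to be.

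The plan also calls the differences exploratory while letting them set the primary model. With no candidate list, two analysts who both follow the text can fit different primary models, and the covariate set can change between the two interims and the final analysis. In an open-label trial, that choice is better closed in advance.

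At stake are a modest amount of power and a small share of trials in which the verdict depends on an unwritten choice.

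**Working it through.** **Reproducing the plan's figure.** Inputs from Sample Size: HR 0.70, two-sided alpha 0.05, power 0.80, overall incidence 25.5%, withdrawal 5%.
- Events (Schoenfeld): 4 × (1.960 + 0.842)² / (ln 0.70)² = 246.8, so 247.
- Patients: 247 / 0.255 = 968.6, so 969; 969 / 0.95 = 1,020. This matches the plan.
- The stated 260 events are 1,020 × 0.255 = 260.1. Power at 260 events is 82.0%. This is an unadjusted calculation.

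**How often the rule fires.** With 510 per arm, the SE of a standardised difference is √(2/510) = 0.0626.
- P(|difference| > 0.1) = 2 × [1 − Φ(0.1/0.0626)] = 2 × [1 − Φ(1.597)] = 0.110.
- At least one of 5 independent candidates: 1 − 0.890⁵ = 0.44. Of 9: 1 − 0.890⁹ = 0.65.

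**At the interims.** Assume uniform accrual over the planned 2 years and the planned event rates. Then about 579 patients are enrolled at 86 events and 916 at 172. The SE is √(4/579) = 0.083 and √(4/916) = 0.066, so the crossing probability per covariate is 23% and 13%. In 20,000 simulated runs with 5 independent candidates, the set at one or both interims differed from the final set in about 70% of trials (89% with 9).

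**Power.** Simulation, 6,000 runs per cell: 1,020 patients, permuted blocks within 26 centres, control incidence 30%, 5% withdrawal, about 260 events, one final test at two-sided 0.05, unadjusted HR held at 0.70. The following are assumptions:
- the covariate distributions, drawn from a plausible TAVI population and then filtered by the eligibility criteria;
- a centre SD of 0.3 on the log-hazard;
- equal standardised coefficients, scaled to a total log-risk SD of 0.3, 0.6 or 0.8.

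| Prognostic factors | Log-risk SD | Log-rank | 0.1 rule | Fixed five fields | Gain over rule |
|---|---|---|---|---|---|
| The five fields only | 0.3 | 81.9% | 81.5% | 82.3% | 0.8 |
| | 0.6 | 82.3% | 83.0% | 85.7% | 2.8 |
| | 0.8 | 81.5% | 82.3% | 88.7% | 6.4 |
| Nine, list holds five | 0.3 | 82.0% | 81.8% | 82.3% | 0.5 |
| | 0.6 | 81.4% | 82.3% | 83.9% | 1.6 |
| | 0.8 | 83.1% | 84.3% | 86.5% | 2.1 |

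The four added factors are atrial fibrillation, haemoglobin, NT-proBNP and prior infarction, all in the baseline table but not entered at randomisation. Gains are paired on the same data (SE 0.2 to 0.4 points) and come from unrounded values. A separate check of the fixed-list gain gave about 0.5, 2.3 and 5.9 points at the three strengths.

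**Error and precision.** Type I error: log-rank 4.2–5.2%, rule 4.0–4.8%, fixed list 4.1–5.1%. SE of the log HR: 0.126 unadjusted, 0.126 under the rule, 0.127 with the fixed list. Mean HR: 0.70 unadjusted, 0.67–0.70 with the fixed list. The gain therefore comes from an estimate further from 1, not from a narrower interval.

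**Effect of the unwritten choices.** Under HR 0.70, the log-rank and the rule-based Cox test disagree at 0.05 in 2.0–5.1% of trials. Two analysts applying the rule to 5 and to 9 candidates reach opposite verdicts in 1.0%, 2.1% and 2.6% of trials at the three strengths. Taking whichever of log-rank and rule-based Cox is significant gives type I error of 4.6–5.7%.

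**The case against.** The strongest reply is that the planned inference is not harmed. The rule holds its error rate, and its power is 81.5% or more in every cell, above the planned 80%. What is lost is power beyond the plan. This stands, and it makes the point an improvement rather than a repair.

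The 6-point end also needs strong factors. If the five are independent, a log-risk SD of 0.8 means 0.8/√5 = 0.358 each, or HR 1.43 per SD. For a 50/50 factor such as sex that is exp(0.358/0.5), an HR of about 2.05, with nothing else prognostic. This stands too. If other collected factors matter, the gain is 0.5 to about 2 points.

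A pragmatic trial sized on a log-rank test may also legitimately target the unadjusted effect. On a natural reading the log-rank tests and the Cox model only estimates, in which case the rule decides no verdict. That reading is open but unwritten, and the rule would still shape the reported hazard ratio.

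Three stronger readings are tempting and are not supported:
- That data-driven selection inflates type I error. Applied mechanically, it does not.
- That the trial is underpowered under the rule. Treating 0.70 as the covariate-conditional HR gives unadjusted power as low as 69.5% and a 12-point gain with very strong factors (HR 1.57 per SD each). But the plan attaches 0.70 to a log-rank comparison, which is unadjusted, and on that basis power stays at the planned level.
- That the plan names no test. It names one, for sizing; what is missing is a sentence tying it to the primary analysis.

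**Conclusion.** The concern holds as a matter of pre-specification and modest efficiency, and should be fixed. Covariate entry depends on chance imbalance among unlisted factors, and at least one of 5 (9) independent candidates would enter in about 44% (65%) of trials. Those rates describe how often the model changes, not how often the conclusion is wrong. Compared with a fixed list, the rule forgoes under 1 point of power if the factors are weak and about 2 to 3 if moderate. It forgoes up to about 6 only if the five fields are strong and are the only prognostic factors. These sizes rest on assumed prognostic strength, assumed covariate distributions and an unadjusted HR of 0.70. The crossing probability rests only on the planned 510 per arm and, for the 44% and 65%, on independence of the candidates.

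**What to change.** Before any arm-level data are seen:

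1. Delete the 0.1 rule. Use one fixed covariate set in the primary Cox model at both interims and the final analysis: diabetes, LVEF, creatinine, age and sex, as entered at randomisation, with the continuous variables kept continuous. The baseline table records LVEF both before and after TAVI, so state which measurement the randomisation field holds.
2. State that the treatment p-value from this model is the deciding test at each look.
3. Report the unadjusted HR and the log-rank test as sensitivity analyses.
4. Keep standardised differences descriptive.

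If the sponsor keeps the log-rank as the deciding test, the plan should say so. The fixed list should still replace the rule for the adjusted HR, but no power gain should then be claimed.

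The cost is analysis wording and a few decisions on coding; no new data and no change to the 1,020 patients. The downside is that the adjusted HR is conditional on the covariates (about 0.67–0.70 when the unadjusted HR is 0.70) and its confidence interval is not narrower.
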